**[name]**

**26th March 2020**

**IRB# 20-003995**

**NCT04459338**

## **Abstract**

Glucagon is an important insulin secretagogue in the concentrations found within the islet.  $\alpha$ -cell dysfunction as occurs in T2DM, in prediabetes or in response to FFA elevation results in increased glucagon concentrations. In these conditions glucagon signals through the GLP-1 receptor (GLP1R) present on  $\beta$ -cells but its net contribution to insulin secretion is unknown. In this experiment we will determine the contribution of GLP-1R signaling to glucagon-induced insulin secretion *in vivo*. To do so, we will use a dose-response experiment for glucagon-stimulated insulin secretion. The experimental conditions will then examine how glucagon-stimulated insulin secretion is modified by blockade of GLP1R blockade using exendin-9,39. This approach will complement other experiments using a glucagon bolus known to stimulate  $\beta$ -cell function in the presence and absence of GLP1R blockade.

## **I. Hypothesis and Specific Aims**

Glucagon within the islet can signal the  $\beta$ -cell through GLP1R, and acts as an insulin secretagogue. This signaling is blocked by exendin-9,39. The relative importance of glucagon signaling through its cognate receptor or through GLP1R is unknown. Despite the lower affinity of GLP1R for glucagon, intra-islet concentrations of glucagon are sufficiently high to stimulate GLP1R^3. The other situation where this may occur is in response to pharmacologic doses of glucagon as used for  $\beta$ -cell function testing or raising peripheral glucagon concentrations above fasting values. **The experiments proposed will characterize the role of GLP1R in glucagon's actions on the  $\beta$ -cell and the potential therapeutic role of dual (GLP-1R and glucagon receptor) agonists for the treatment of T2DM and obesity.** The experiments will also provide an opportunity to test glucagon's actions on insulin secretion, independently of glucose concentrations.

**We will therefore address the following specific aim: -**

**Specific Aim:** Determine the contribution of GLP1R to glucagon-stimulated insulin secretion.

**1° Hypothesis:** Glucagon-stimulated insulin secretion is decreased by GLP1R blockade with exendin-9,39

**2° Hypotheses:** The contribution of GLP1R to glucagon-stimulated insulin secretion is more significant at higher glucagon concentrations

[figure not shown]
## **II. Background and Significance**

Diabetes mellitus causes morbidity, mortality and costs in excess of ~\$170 billion/year. The discovery of gut-derived proglucagon peptides, most specifically GLP-1, has fueled therapeutic innovations for T2DM. Proglucagon is transcribed and translated from the glucagon gene (GCG) but its final fate depends on concomitant expression of prohormone-convertase (PC) enzymes. PC-1/3 is expressed in intestinal L-cells resulting in production of GLP-1. On the other hand, PC-2 is expressed in  $\alpha$ -cells so that glucagon is the main derivative of proglucagon produced by these cells. However, PC-1/3 expression is inducible, suggesting that extra-intestinal synthesis and secretion of GLP-1 is possible. IL-6, hyperglycemia and FFA seem to increase PC-1/3 expression in islets. **This raises the possibility that pancreatic production of GLP-1 modulates islet function in response to glucolipotoxicity and other metabolic stressors.**

In pharmacologic concentrations, GLP-1 is a powerful insulin secretagogue. It also inhibits glucagon secretion, delays gastrointestinal transit and decreases appetite. Endogenous concentrations of active GLP-1 are much lower and transient, partly due to the ubiquity of DPP-4. Considerable GLP-1 degradation occurs close to its site of production resulting in a circulating  $T_{1/2} \sim 1\text{min}^{26}$ . This may explain why inhibition of GLP-1 actions at GLP1R using a competitive antagonist (exendin-9,39) has little effect on postprandial glucose metabolism. Indeed, only one study to date has shown a post-prandial effect of exendin-9,39 in healthy humans and this can be explained by increased gastric volume prior to meal ingestion. On the other hand, after bariatric surgery when endogenous GLP-1 concentrations are raised several-fold, inhibition of GLP-1 action impairs insulin secretion and raises glucose concentrations slightly, but significantly.

However, the implication that endogenous GLP-1 is of little relevance outside of bariatric surgery, is at odds with the conservation of the GLP-1 sequence across vertebrates. GLP-1 may also contribute to the 'incretin effect' – the potentiation of post-prandial insulin secretion by gut (as opposed to I.V.) nutrient delivery. Salehi et al. reported that endogenous GLP-1 enhances postprandial insulin secretion. However, the experiment

utilized a hyperglycemic clamp as opposed to the transient meal (or meal-like) challenges in our experiments (**Fig.1**). More germane to this proposal, they also observed an effect of GLP1R blockade on insulin secretion in response to intravenous glucose alone.

that islet GLP-1 expression increases with the development of diabetes. It is also notable that exposure of islets to FFA and hyperglycemia also increases GLP-1. Our published and unpublished (**Fig.1**) preliminary data, as well as genetic data shows that GLP-1 signaling through its cognate receptor in the fasting state (or during an intravenous glucose challenge) plays a role in islet function. **Understanding the physiologic role of GLP-1 secretion independently of oral intake in humans will allow us to better modulate this pathway and prevent / treat islet dysfunction in prediabetes and T2DM.**

[figure not shown]
The other consideration is that glucagon within the islet can signal the  $\beta$ -cell through GLP1R, and acts as an insulin secretagogue. This signaling is blocked by exendin-9,39. The relative importance of glucagon signaling through its cognate receptor or through GLP1R is unknown. Despite the lower affinity of GLP1R for glucagon, intra-islet concentrations of glucagon are sufficiently high to stimulate GLP1R^3. The other situation where this may occur is in response to pharmacologic doses of glucagon as used for  $\beta$ -cell function testing or raising peripheral glucagon concentrations above fasting values. **The experiments proposed will characterize the role of GLP1R in glucagon's actions on the  $\beta$ -cell and the potential therapeutic role of dual (GLP-1R and glucagon receptor) agonists for the treatment of T2DM and obesity.**

Glucagon dysregulation is likely to be an earlier contributor to the pathogenesis of T2DM than has been appreciated. More significantly, although I.V. administration of glucagon is used as a test of  $\beta$ -cell function, its role as an insulin secretagogue within the islet has been overlooked. Glucagon can signal the  $\beta$ -cell through GLP1R in addition to the glucagon receptor (and its action blocked by exendin-9,39). What role does this play in physiology and in T2DM? The experiments proposed will quantify the effects of exendin-9,39 on glucagon-stimulated insulin secretion. Complementary experiments will also explore whether glucagon-stimulated insulin secretion is altered by rs3765467, by T2DM and by acute FFA elevation to mimic metabolic stress.

Infusion of exendin-9,39 to block GLP1R during an intravenous glucose challenge (that mimics the systemic appearance of a meal) impairs  $\beta$ -cell function in non-diabetic humans with little effect on glucagon secretion (**Fig.1a,c**). Similar effects are observed in cadaveric islets from people without T2DM (**Fig.2**). Conversely, in people with T2DM (**Fig.1b,d**) or in islets isolated from diabetic humans (**Fig.5**), there is no effect of exendin-9,39 on  $\beta$ -cell function, perhaps due to the degree of  $\beta$ -cell dysfunction. However, in T2DM, exendin-9,39 raises fasting glucagon and impairs its suppression by intravenous glucose *in vivo* (**Fig.4**). **Our preliminary data also suggests that GLP-1 contributes to islet function outside the postprandial period; the effects differ in T2DM compared to non-diabetic subjects (Fig.1).**

Although the source of fasting GLP-1 secretion is uncertain, complementary experiments in isolated human islets (and the literature) strongly suggest an islet source for GLP-1 (**Fig.2**). O'Malley et al. have suggested

[figure not shown]
### III. Preliminary Data

**Figure 2:** Acute GLP1R blockade with Ex-9,39 in isolated human cadaveric islets (obtained from Prodo labs) from non-diabetic subjects (ND) decreased insulin secretion in response to hyperglycemia. This was not apparent in T2DM. Glucose-stimulated insulin secretion was assessed by static incubation of islets at low (4mM) and high (16mM) glucose  $\pm$  100nM Ex-9,39. Insulin Stimulation Index represents fold change in insulin secretion at 16/4 mM glucose. \* $p<0.05$  ( $n=3$  technical repeats).

insulin secretion using a range of glucagon infusion rates.

#### IV. Research Design and Methods

**Figure 3:** Experimental Design

We and others have shown that GLP-1 in the postprandial period has little effect on post-prandial insulin secretion outside of RYGB. Intriguingly, a variant in GLP1R that increases response to GLP-1 has been shown to decrease risk of T2DM and lower fasting glucose. Also, DPP-4i which raise postprandial concentrations of active GLP-1 also lower fasting glucose concentrations, suggesting that fasting GLP-1 secretion alters islet function. The literature and our preliminary data (**Fig.1,2**), suggest a pancreatic source for GLP-1.

T2DM, inflammation and metabolic stress increase islet expression of GLP-1, perhaps as an adaptive function to preserve  $\alpha$ - and  $\beta$ -cell function. Blockade of GLP1R with exendin-9,39 seems to have divergent effects in people with and without T2DM (**Fig.4,7**), perhaps because of the degree of  $\beta$ -cell dysfunction present (**Fig.4,5**). In **Specific Aim 2** (**Fig.9**) we will characterize differences (in people with and without T2DM) in islet function during fasting and hyperglycemic conditions attributable to endogenous GLP-1. We will also alter fasting FFA concentrations to examine the role of GLP-1 during metabolic stress in people without T2DM.

Glucagon is a known insulin secretagogue. Within islets, glucagon can act on the  $\beta$ -cell through GLP1R in addition to its cognate receptor. The experiments will provide an opportunity to characterize the GLP1R contribution to glucagon-stimulated insulin secretion using a range of glucagon infusion rates.

**Study Subjects:** After approval from the Mayo Clinic Institutional Review Board, we will recruit 20 weight-stable, otherwise healthy subjects between the ages of 18-65, using local advertising and other methods employed previously. Subjects will have no history of active disease or diabetes. Individuals who have expressed interest in participating in research will also be contacted and invited to participate in the study.

**Screening Visit:** After an overnight fast of 8 hours, subjects will present to the Clinical Research Trials Unit (CRTU) at approximately 0700. Subjects will provide written, informed consent. To ensure they are otherwise healthy,

subjects will undergo a history and limited physical examination; blood collection for complete blood count, fasting glucose, HbA1c, sodium, potassium, creatinine and urine collection to exclude pregnancy. An ECG will also be performed. The Minnesota Leisure-Time Physical Activity questionnaire will be used to assess habitual activity levels. **Body Composition:** After informed written consent is obtained, body composition will be measured at the screening visit using dual-energy X-ray absorptiometry (iDXA scanner; GE, Wauwatosa, WI). All subjects will be instructed to follow a weight-maintenance diet (55% carbohydrate, 30% fat and 15%

protein) for at least 3 days prior to each study. **Screening OGTT:** At approximately 0900 subjects will ingest 75g glucose. Arterialized venous blood will be sampled over 2 hrs. Glucose values at 0 and 120 minutes will be used to categorize glucose tolerance status. Subjects who have had a DEXA or OGTT in the last 3 months as part of the [name] Lab research studies or another Mayo research group, and weight is stable (+) or (-) 5 pounds, will not be retested and previously obtained values will be used.

We will study 20 subjects a total of 2 times at least a week apart in random order. All subjects will be admitted to the Mayo Clinic CRTU at 1700 hours the evening before the study. Women who could become pregnant will have a urine collection for point of care pregnancy testing. Following ingestion of a standard 10 kcal/kg caffeine-free meal, subjects will fast overnight. The following morning at approximately 0530 (-210 min), a dorsal hand vein will be cannulated and placed in a heated Plexiglas box maintained at 55°C to allow sampling of arterialized venous blood. The contralateral forearm vein will be cannulated for glucose, and hormone infusions. At approximately 0600 (-180 min), a primed, (10 $\mu$ Ci prime, 0.1 $\mu$ Ci/min continuous) infusion containing trace amounts of glucose labeled with [3-H] glucose will be started and continued till 0900 (0 min). Subsequently, the infusion will be varied so as to mimic the anticipated pattern of fall of EGP to minimize changes in Specific Activity. At that time another glucose infusion, also labeled with [3-H] glucose will commence and infusion rate varied so as to produce peripheral glucose concentrations of ~160mg/dL. A glucagon infusion at 0.4ng/Kg/min will start at 0900 (0 min), increasing by 0.2ng/kg/min every hour (**Fig.3**). Blood will be sampled till the end of the study (1400 – 300 min) when I.V. cannulas will be removed; participants will consume a late lunch and leave the CRTU. This will be referred to as the saline (**Sal**) day because 0.9% Saline will be infused between 0 and 300 min. On another study day, exendin-9,39 (**Exe**) will be infused at 300pmol/kg/min between 0 and 300 min.

**Analytical Techniques:** All blood will be immediately placed on ice, centrifuged at 4°C, separated and stored at -80°C until assay. Glucose will be measured using a Yellow Springs glucose analyzer. Glucagon will be collected in protease inhibitor-containing tubes (BD800, BD Franklin Lakes, NJ) and measured using an ELISA (Mercodia, Winston-Salem, NC). C-peptide will be measured using EMD Millipore (Billerica, MA) reagents. Insulin will be measured using a chemiluminescence assay with reagents obtained from Beckman (Access Assay, Beckman, Chaska, MN). Total and Intact GLP-1 will be collected in protease inhibitor-containing tubes (BD800, BD Franklin Lakes, NJ) and measured using an ELISA (ALPCO Diagnostics, Salem, NH). [3-H] glucose specific activity will be measured by liquid scintillation counting after deproteinization and passage over anion- and cation-exchange columns.

**Calculations:** In addition to fasting, peak and nadir hormone concentrations, we will calculate area above basal (AAB) or area under the curve (AUC) during the experiment using the trapezoidal rule as previously described.  $S_i$ , Insulin Secretion Rate (ISR) and  $\beta$ -Cell responsivity ( $\Phi$ ) indices will be calculated from the glucose, insulin and C-peptide concentrations observed during the experiments using the minimal model, incorporating age-associated changes in C-peptide kinetics.  $\Phi$  is derived from the sum of  $\phi_1$  (1st phase insulin secretion) and  $\phi_2$  (2nd phase insulin secretion) as before. Disposition index (DI) will express  $\beta$ -cell function as a function of the prevailing insulin action. Glucose disappearance (Rd) will be calculated using steady state Steele equations after Specific activity is smoothed as previously described. Endogenous glucose production (EGP) will be calculated as the difference between the tracer determined rate of glucose appearance and the glucose infusion rate. All infusion rates will be expressed as Kg per lean body mass.

Power Calculation	Mean $\pm$ SD	Detectable difference
1° hypothesis (n = 20 - paired)		
$\Phi$ (10 $^{-9}$ min $^{-1}$ ) - hyperglycemia	149 $\pm$ 45	30 (20%)

Table 1: Means  $\pm$  SD used to estimate power

**Statistical Analysis:** A paired 2-tailed student *t*-test (parametric) or a Wilcoxon rank-sign test (non-parametric) will be used to examine differences between **Sal** and **Exe** days for the 1° hypothesis (**Table 3**).

**3) Power Calculation:** Please refer to **Table 3**.

**3) Interpretation:** If glucagon stimulates insulin secretion by acting, at least partially, through GLP1R we would expect that exendin-9,39 will decrease the response to glucagon by blocking GLP1R. To test our 1° hypothesis, we will compare  $\Phi$  during each glucagon infusion rate in the presence and absence of exendin-9,39. Assuming that glucagon concentrations as encountered in the islet are necessary to stimulate insulin secretion via GLP1R, we expect differences to be more marked at the higher glucagon infusion rates (2° hypothesis). The experiments will be conducted in relatively lean, healthy and insulin sensitive humans. Under these experimental conditions, we expect EGP to be suppressed and insulin secretion stimulated by hyperglycemia and glucagon infusion. The rising infusion rates of glucagon will enable us to examine the

effects of the latter on endogenous glucose production (EGP) and endogenous insulin secretion in the presence and absence of GLP1R blockade.

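### The glucagon rate rises in one fixed order while exendin runs throughout, so a Sal–Exe difference that grows across steps cannot be attributed to glucagon concentration rather than duration of exendin exposure

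*Combined protocol and SAP*

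**What the plan says.** The study-day description in section IV sets the glucagon steps: "A glucagon infusion at 0.4ng/Kg/min will start at 0900 (0 min), increasing by 0.2ng/kg/min every hour". The study ends at 300 min, so there are five hourly steps: 0.4, 0.6, 0.8, 1.0 and 1.2 ng/kg/min.

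The other infusions share the same clock. A labelled glucose infusion starts at 0 min with its "infusion rate varied so as to produce peripheral glucose concentrations of ~160mg/dL". On one day, "This will be referred to as the saline (Sal) day because 0.9% Saline will be infused between 0 and 300 min". On the other, "exendin-9,39 (Exe) will be infused at 300pmol/kg/min between 0 and 300 min". Only the order of the two days is randomised. The text describes no other step order, no time control and no exendin run-in. Figure 3 is not shown, but the text cites it for this same schedule.

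The 2° hypothesis in section I is: "The contribution of GLP1R to glucagon-stimulated insulin secretion is more significant at higher glucagon concentrations". The Interpretation paragraph of section IV says how it will be read: "we expect differences to be more marked at the higher glucagon infusion rates (2° hypothesis"). The Statistical Analysis paragraph names a paired t-test or Wilcoxon test for the 1° hypothesis only. No test, model or time adjustment is given for the 2° hypothesis.

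**The concern.** The 1° hypothesis asks whether Φ differs between days at a given step. The 2° hypothesis asks whether that difference changes from step to step, which is a treatment-by-step interaction. Pairing the days removes anything that evolves equally on both. It does not remove an exendin effect that itself changes with time, for example while blockade is being established or as hyperglycaemia continues under blockade.

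Such an effect is possible without any role for infused glucagon. Section II reports impaired β-cell function in non-diabetic people with "Infusion of exendin-9,39 to block GLP1R during an intravenous glucose challenge", and mentions no glucagon infusion there. In this trial exendin, glucose and glucagon all start at the same minute, so the lowest glucagon step is also the step with the least exendin exposure.

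At stake is the secondary, mechanistic conclusion. A growing difference would be taken to show a concentration-dependent GLP1R contribution when the data are equally compatible with duration of exposure.

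**Working it through.** **The plan's own figure.** Table 1 gives Φ = 149 ± 45, n = 20 paired, detectable difference 30. Alpha and power are not stated. Assuming two-sided 0.05 and 80% power, and taking 45 as the SD of the paired difference, the noncentral t with 19 df gives a detectable difference of 29.7 and 80.7% power at 30. The figure reproduces, and this point does not affect it.

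**Identifiability.** Let h = 0, 1, 2, 3, 4 be the hours elapsed at the start of each step, so rate = 0.4 + 0.2h. Write the expected Sal–Exe difference as

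d(h) = a + b × rate + g × h,

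where b is dependence on glucagon rate and g is dependence on exposure time. Substituting,

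d(h) = (a + 0.4b) + (0.2b + g)h.

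Only the sum 0.2b + g can be estimated. The correlation of rate with time across steps is exactly 1. Equivalently, take the ten day-by-step cells with terms for intercept, exendin, rate, time, exendin × rate and exendin × time. The design matrix has rank 4 of 6, and the two interactions cannot be separated. A time trend shared by both days drops out of d(h) and does no harm.

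**Size, as an illustration.** The following are assumptions, not statements in the plan:

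- The SD of the Sal–Exe difference at each step is 45.
- The correlation ρ between steps is 0.5 to 0.7.
- The exendin effect does not depend on glucagon and equals 30 × (1 − exp(−t/τ)), evaluated at step midpoints t = 30, 90, 150, 210, 270 min.
- The test is a linear contrast with weights −2, −1, 0, 1, 2, two-sided 5%, counted only in the hypothesised direction.

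Let L be the contrast of the five step effects. The SD of one subject's contrast is 45 × √(10(1 − ρ)), which is 100.6 at ρ = 0.5 and 77.9 at ρ = 0.7. The noncentrality is L × √20 / SD.

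| τ (min) | Step effects | L | False positive, ρ = 0.5 | ρ = 0.7 |
|---|---|---|---|---|
| flat effect of 30 | 30, 30, 30, 30, 30 | 0 | 2.5% | 2.5% |
| 10 | 28.5, 30.0, 30.0, 30.0, 30.0 | 3.0 | 3% | 4% |
| 30 | 19.0, 28.5, 29.8, 30.0, 30.0 | 23.5 | 17% | 25% |
| 60 | 11.8, 23.3, 27.5, 29.1, 29.7 | 41.5 | 42% | 62% |
| 120 | 6.6, 15.8, 21.4, 24.8, 26.8 | 49.4 | 55% | 77% |

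For τ = 60 and ρ = 0.5, for example, the noncentrality is 41.5 × 4.472 / 100.6 = 1.85, which gives 42%.

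**Can within-step drift settle it?** While the rate is constant, a drifting Sal–Exe difference might seem to isolate the time effect. It does not, because a lagged glucagon response drifts too. Suppose the difference is driven entirely by glucagon, rises by 6 per step and lags with a 30-min time constant. In the second half of the first step it changes by 6 × (e⁻¹ − e⁻²) = 6 × (0.368 − 0.135) = 1.4, or about 2.8 per hour. Nearly half of a genuine 6-unit step would be charged to time.

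**The case against.** The strongest reply is that the documents show no exendin effect that builds with time. The background finding under intravenous glucose fits a constant effect equally well, and a constant effect leaves the trend test at its nominal 2.5%. Endogenous glucagon was also present in that experiment, so it does not demonstrate an effect free of glucagon. This stands: the plan does not show that a time effect exists, only that it could not be recognised.

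Second, the percentages rest on an assumed onset and on a test that is not in the plan. With fast onset the problem is negligible. Using only the second half hour of each step would also lower the figures, to 28–43% at τ = 60 min and 9–13% at τ = 30 min. This stands too, which is why the whole range is shown. The aliasing itself depends on none of these choices.

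Third, measured glucagon varies between subjects within a step and could add some non-randomised information. That is true, but no such analysis is planned.

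A reader might infer several stronger things that the documents do not support:

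- *That the 1° hypothesis is compromised.* At each step the two days are matched on rate and elapsed time.
- *That duration of hyperglycaemia alone confounds the result.* It is common to both days. Only an exendin effect that changes with it survives the pairing.
- *That the bias must favour the hypothesis.* Φ includes first-phase secretion, and the rise to the glucose target falls in step 1. A first-phase exendin effect could enlarge the step-1 difference and work against the hypothesis.

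**Conclusion.** The point holds for the 2° hypothesis only. On the schedule as written, glucagon rate and duration of exendin exposure are perfectly aliased in the Sal–Exe difference across steps, and no analysis of the planned rates separates them. This follows from the text and needs no assumption.

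The practical size is uncertain. It runs from about 3% to 77% false trends in the hypothesised direction for assumed time constants of 10 to 120 min, given an assumed SD of 45, between-step correlation 0.5–0.7 and an effect building to 30. These are illustrations of what could happen, not the plan's error rate, because the plan states no onset time, no sampling interval and no test for this hypothesis. The planned reading of a growing difference as dependence on glucagon concentration should be changed, because the design cannot support that specific claim.

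**What to change.** Leave the infusions and the 1° comparison as they are. In the Interpretation paragraph of section IV, reword the 2° reading, for example: *A Sal–Exe difference that grows across the steps will be reported as an effect of glucagon rate or duration of exposure. Because the rates rise in one fixed order on both days, the design does not separate the two, and the result is not evidence specific to glucagon concentration.*

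The time course of the Sal–Exe difference in ISR within each step may be shown descriptively beside this, as far as the sampling allows. It should not serve as a pass/fail rule, for the reason given in the check on within-step drift.

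The cost is a few sentences and, if wanted, one descriptive figure from ISR already planned. The downside is a weaker 2° claim.

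### Rd is assigned a steady-state equation over a period in which glucose is driven up to ~160 mg/dL, so first-hour Rd is overstated; EGP is at risk only if specific activity drifts differently on the two days

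*Combined protocol and SAP*

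**What the plan says.** All the relevant text is in the combined protocol and SAP, section IV (Research Design and Methods).

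- **Rd.** The Calculations paragraph states: "Glucose disappearance (Rd) will be calculated using steady state Steele equations", applied "after Specific activity is smoothed as previously described". It gives no pool volume, pool fraction or analysis window.
- **EGP.** The same paragraph states: "Endogenous glucose production (EGP) will be calculated as the difference between the tracer determined rate of glucose appearance and the glucose infusion rate". Rd is not an input, and no equation is named for Ra.
- **Glucose.** The study-day text starts a glucose infusion at 0 min, with its "infusion rate varied so as to produce peripheral glucose concentrations of ~160mg/dL". The glucagon infusion starts at the same time and is stepped up hourly until 300 min.
- **Specific activity (SA).** Two measures are planned to hold it steady. For the tracer: "Subsequently, the infusion will be varied so as to mimic the anticipated pattern of fall of EGP to minimize changes in Specific Activity". The infused glucose also carries tracer: "At that time another glucose infusion, also labeled with" the same isotope.
- **Use.** The Interpretation paragraph says that the rising glucagon rates will allow the team to examine the "effects of the latter on endogenous glucose production (EGP) and endogenous insulin secretion in the presence and absence of GLP1R blockade". No test or power is given for EGP or Rd.

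**The concern.** The steady-state equation is valid for Rd only when the glucose pool is not changing size. Here the pool is enlarged deliberately from 0 min, so part of the glucose appearing in hour 1 fills the pool and is not disposed of. Equating Rd with Ra counts that part as disposal.

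Holding SA constant does not help, because the missing term depends on the rate of change of glucose and not on SA. Smoothing SA removes noise but does not supply the term.

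Glucagon rate and time rise together in this design, so an error confined to the first hour falls entirely on the lowest glucagon step. Rd tabulated by step would then show a false pattern across glucagon rates within each study day. EGP raises a separate and weaker question, which depends on how well SA is controlled on each day.

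**Working it through.** **The plan's own figure.** The only computed figure is the detectable difference in Φ (Table 1): 30, or 20%, with n = 20 paired, mean 149 and SD 45. Taking 45 as the SD of the paired difference, with two-sided alpha 0.05 and 80% power (neither is stated), the paired t-test gives 29.7, and 30/149 = 20.1%. The figure reproduces, and neither Rd nor EGP enters it.

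**Equations.** With G = glucose, F = total tracer infusion and pV = effective pool:

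- Non-steady state: Ra = F/SA − pV·G·(dSA/dt)/SA, and Rd = Ra − pV·dG/dt.
- Steady state: Rd = Ra = F/SA.
- Error in Rd from the steady-state form: pV·dG/dt + pV·G·(dSA/dt)/SA.
- Error in EGP if Ra is also taken as F/SA: pV·G·(dSA/dt)/SA only.

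**Size of the Rd error with SA flat.** The target of 160 mg/dL is from the protocol. Fasting glucose (90 mg/dL) and pV (1.0 to 1.6 dL/kg) are assumptions. If the target is reached within the hour, the hour-1 mean depends only on the end points:

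| pV (dL/kg) | pV × (160 − 90)/60 (mg/kg/min) |
|---|---|
| 1.0 | 1.17 |
| 1.3 | 1.52 |
| 1.6 | 1.87 |

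With fasting glucose of 80 to 100 mg/dL and pV of 1.0 to 2.0 dL/kg, the range is 1.0 to 2.7.

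**One-pool simulation, 0 to 300 min.** Assumed inputs: pV 1.3 dL/kg; glucose from 90 to 160 mg/dL with time constant 12 min; EGP from 2.0 to 0.6 mg/kg/min on Sal and to 1.0 on Exe (time constant 30 min); Rd from 2.0 to 6.0 on Sal and to 5.0 on Exe (time constant 90 min).

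1. *Sal, tracer matched to EGP (SA flat).* Hour-1 Rd is overstated by 1.51 on a true 3.08 (49%), and hour-2 Rd by 0.01 on 4.50. Steady-state Rd therefore reads 4.59 then 4.51, where the truth is 3.08 then 4.50. With a slow rise (time constant 30 min) the errors are 1.31 and 0.18. The EGP error is 0.00 in every hour.
2. *Exe, tracer matched to that day's EGP.* The hour-1 Rd error is again 1.51, so it cancels in the Sal–Exe contrast. The EGP error is 0.00 in every hour.
3. *Exe, run with the Sal tracer pattern.* SA falls about 5% in hour 1 and 8 to 9% overall. Results for EGP (mg/kg/min):

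| | Hour 1 | Hour 2 |
|---|---|---|
| True Exe − Sal difference | 0.23 | 0.38 |
| EGP error on Exe | −0.16 | −0.12 |
| Difference as computed | about 0.07 | about 0.26 |

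From hour 3 the EGP error is within 0.03. The hour-1 Rd error on Exe becomes 1.35 instead of 1.51, so the Rd contrast is also off by 0.16.

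**If glucose rises differently on the two days.** The hour-1 Rd contrast is off by pV × (difference in rise)/60. A 5 mg/dL difference with pV 1.0 gives 0.08, and a 10 mg/dL difference with pV 1.6 gives 0.27 mg/kg/min.

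**EGP error per unit of SA drift.** At 160 mg/dL with pV 1.3, a drift of 5% per hour gives 1.3 × 160 × 0.05/60 = 0.17 mg/kg/min, and 10% per hour gives 0.35.

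**The case against.** The strongest reply is that the design already deals with non-steady conditions. The tracer is tapered, the infused glucose is labelled, and SA is smoothed. With SA flat, the steady-state and non-steady-state forms give the same Ra, so EGP is right even while glucose and EGP move. This stands for EGP. It does not stand for Rd, whose missing term is unrelated to SA.

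A reader might infer that the Sal–Exe EGP contrast will be distorted. The documents do not support that. The steady-state sentence concerns Rd, and EGP is not derived from Rd. The distortion in case 3 needs two things the protocol does not state: one preset tracer pattern used on both days, and a change in EGP suppression with exendin. The text speaks of an anticipated pattern without saying whether it is set separately for each day. The EGP risk is therefore conditional, although the plan gives no SA tolerance or fallback equation if drift occurs.

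It is also fair to say that Rd carries no hypothesis or test, that its error largely cancels between days, and that Rd may be meant for the plateau only. One cited Steele reference is titled for an oral glucose tolerance test, so the phrase may be loose wording. These points lower the importance. They do not remove the need to correct the text, which names one equation and gives no window.

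**Conclusion.** The point holds for Rd. Followed as written, the plan overstates mean hour-1 Rd by about 1.2 to 1.9 mg/kg/min (fasting glucose 90 mg/dL, pV 1.0 to 1.6 dL/kg, target reached within the hour), with almost no error once glucose is at plateau. The error affects Rd levels and their pattern across glucagon steps within a day. It affects the Sal–Exe contrast only so far as the glucose rise or the SA drift differs between days.

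For EGP there is a conditional risk in hours 1 and 2, and no error if SA is held flat. Φ is obtained from glucose and C-peptide, so the primary comparison and the sample size are untouched. Severity is minor. Fasting glucose, pV, the speed of the rise, and the EGP and Rd levels are all assumptions; the documents give none of them.

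**What to change.** In Calculations, name the non-steady-state Steele form for 0 to 300 min:

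- Ra = F/SA − pV·G·(dSA/dt)/SA, with F the total tracer infusion, including the tracer in the labelled glucose infusion;
- Rd = Ra − pV·dG/dt;
- EGP = Ra − glucose infusion rate.

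State the pV used and repeat the calculation over a range such as 1.0 to 1.6 dL/kg. Put pV on the same per-kg basis as the infusion rates, which the plan expresses per kg of lean mass. Keep the steady-state form for the baseline before 0 min, where glucose and SA are stable.

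This changes a few lines of analysis text and no study procedure. At plateau with flat SA the two forms agree, so nothing is lost there. The cost is an assumed pool size, covered by the range, and some noise from taking derivatives of smoothed data. The readable text gives no sampling times, so the amount of that noise cannot be judged from the documents.
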